8.2. Subject Disposition and Population Assignment

Subject disposition and population assignment will be listed.

A summary table by treatment sequence will be provided, based on the all subjects population.

8.3. Screening Demographics and Baseline Characteristics

The screening demographics and baseline characteristics including age, sex, race, ethnicity, height, body weight, and body mass index will be listed.

A summary table will be provided, based on the safety population.

8.4. Prior and Concomitant Medication

Prior medication will be defined as medication that ends prior to the first dose. Concomitant medication will be defined as medication that starts during or after the first dose or starts but does not end prior to the first dose.

Prior and concomitant medications will be coded using the World Health Organization Drug Dictionary (WHODrug) Global, Format B3, Version March 2020. Prior and concomitant medications will be listed.

8.5. Pharmacokinetic Assessments

8.5.1. Pharmacokinetic Analysis

The following PK parameters will be determined where possible from the plasma concentrations of caffeine, paraxanthine, omeprazole, S-warfarin, and LOXO-305 (unless otherwise indicated) using noncompartmental methods in validated software program Phoenix WinNonlin (Certara, Version 8.1 or higher):

Parameter	Units ^a	Definition
AUC ₀₋₂₄	h*ng/mL	area under the concentration-time curve from hour 0 to 24 hours postdose ^b
AUC _{0-t}	h*ng/mL	area under the concentration-time curve from hour 0 to the last measurable concentration (t_{last}) ^b
AUC _{0-inf}	h*ng/mL	area under the concentration-time curve from hour 0 extrapolated to infinity ^c (except LOXO-305)
%AUC _{extrap}	%	percentage extrapolation for AUC _{0-inf} (except LOXO-305)
C _{max}	ng/mL	maximum observed plasma concentration
t _{max}	h	time to maximum observed plasma concentration
λ_z	1/h	apparent terminal elimination rate constant (except LOXO-305)
t _{1/2}	h	apparent terminal elimination half-life
CL/F	L/h	apparent systemic clearance (except paraxanthine)
V _z /F	L	apparent volume of distribution at the terminal phase (except LOXO-305 and paraxanthine)
MRT _{inf}	h	mean residence time (based on AUC _{0-inf} , except for LOXO-305)
MRAUC	NA	ratio of paraxanthine AUC to caffeine AUC (based on AUC ₀₋₂₄ and AUC ₀₋₄₈ if possible)

NA Not applicable

^a Units are based on concentration units (provided by the bioanalytical lab or preferred units for presentation of PK parameters) and dose units used in the study.

^b Area under the concentration-time curve will be calculated using the linear trapezoidal rule for increasing and decreasing concentrations

^c Based on the last observed quantifiable concentration

Additional PK parameters may be determined where appropriate.

The PK analysis will be carried out where possible using actual blood sampling times postdose. If an actual time is missing, the sample concentration result will be treated as missing unless there is scientific justification to include the result using the nominal time.

The parameters C_{max} and t_{max} will be obtained directly from the concentration-time profiles. If C_{max} occurs at more than 1 timepoint, t_{max} will be assigned to the first occurrence of C_{max}.

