8.3. Pharmacokinetic Analysis

Serial blood samples for plasma concentration analysis will be analyzed using samples collected at the following timepoints:

- Caffeine/paraxanthine:
 - CCI [REDACTED] following administration alone on [REDACTED]
- Omeprazole:
 - CCI [REDACTED] following administration alone on [REDACTED]
- S-Warfarin:
 - CCI [REDACTED] following administration alone on [REDACTED]
- LOXO-305:
 - CCI following administration alone on CCI [REDACTED]
 - CCI [REDACTED] following administration with CCI [REDACTED]

Whenever possible, the following PK parameters for each substrate (caffeine/paraxanthine, omeprazole, and S-warfarin) and LOXO-305 will be calculated for each subject based on the plasma concentrations (as appropriate):

- area under the concentration time curve (AUC) from hour 0 to 24 hours postdose (AUC₀₋₂₄)
- AUC from hour 0 to the last measurable concentration (AUC_{0-t})
- AUC from hour 0 extrapolated to infinity (AUC_{0-inf})
- percentage extrapolation for AUC_{0-inf} (%AUC_{extrap})
- apparent systemic clearance (CL/F)
- C_{max}
- mean residence time (MRT)
- apparent plasma terminal elimination half-life (t_{1/2}) wherever possible, where t_{1/2} = natural log (2)/λ_Z
- time to maximum observed plasma concentration (t_{max})
- apparent terminal elimination rate constant (λ_Z)
- apparent volume of distribution at terminal phase (V_ZF)
- AUC₀₋₂₄ and AUC₀₋₄₈ ratio of paraxanthine to caffeine (MRAUC; caffeine/paraxanthine only)

Pharmacokinetic calculations will be performed using commercial software such as Phoenix™ WinNonlin® Version 8.1 or higher (Certara USA Inc.).

Other parameters may be added as appropriate. Final PK parameters reported will be detailed in the Statistical Analysis Plan (SAP).

Pharmacokinetic analysis will use actual times as recorded on the eCRF. All statistical analyses will be performed using SAS® Version 9.4 or greater. More details on the analyses will be included in the SAP.

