8.5.1.1. Criteria for the Calculation of Apparent Terminal Elimination Rate Constant and Half-life

The start of the terminal elimination phase for each subject will be defined by visual inspection and generally will be the first point at which there is no systematic deviation from the log-linear decline in concentrations.

The apparent terminal elimination rate constant (λ_z) will only be calculated when a reliable estimate can be obtained using at least 3 data points, preferably not including C_{max}, and the adjusted coefficient for determination of exponential fit (R²-adj) of the regression line is ≥ 0.7 . Parameters requiring λ_z for their calculation (eg, AUC_{0-inf}, t_{1/2}, CL/F, V_z/F, and MRT_{inf}) will only be calculated if the R²-adj value of the regression line is ≥ 0.7 .

The following regression-related diagnostic PK parameters will be determined, when possible:

Parameter	Units	Definition
λ_z Upper	h	end of exponential fit
λ_z Lower	h	start of exponential fit
λ_z N	NA	number of data points included in the log-linear regression
λ_z Span Ratio	NA	time period over which λ_z was determined as a ratio of $t_{1/2}$
R ² -adj	NA	adjusted coefficient for determination of exponential fit

Where possible, the span of time used in the determination of λ_z (ie, the difference between λ_z Upper and λ_z Lower) should be ≥ 2 half-lives. If the λ_z Span Ratio is < 2 , the robustness of the $t_{1/2}$ values will be discussed in the CSR.

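### Do the SAP's parameter rules leave LOXO-305 half-life and CL/F uncomputable, or CL/F about 1.8-fold too low?

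*SAP*

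**What the plan says.** SAP 8.5.1 lists the PK parameters with exclusions by analyte:

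- AUC0-inf is "extrapolated to infinity ^c (except LOXO-305"), and its percentage extrapolation is excluded for LOXO-305 as well.
- λz is "apparent terminal elimination rate constant (except LOXO-305").
- Vz/F is "apparent volume of distribution at the terminal phase (except LOXO-305 and paraxanthine").
- Half-life, "apparent terminal elimination half-life", carries no exclusion.
- CL/F is "apparent systemic clearance (except paraxanthine"), so LOXO-305 stays in. No formula is given.
- AUC0-24 and Cmax are kept for all analytes.

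SAP 8.5.1.1, which covers all analytes, adds: "Parameters requiring λ_z for their calculation (eg, AUC_{0-inf}, t_{1/2}, CL/F, V_z/F, and MRT_{inf}) will only be calculated if the R²-adj value" reaches 0.7. It makes no exception for LOXO-305. Protocol 8.3 defines half-life by the usual relation, "where t_{1/2} = natural log (2)/λ_Z".

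Both documents qualify the whole list. The parameters are to be obtained where possible and as appropriate to the analyte (SAP 3.1 and 8.5.1; protocol 2.2.1 and 8.3).

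**The concern.** For LOXO-305 the table asks for two quantities while withholding the input that the next subsection says they need. Half-life is ln(2)/λz, yet λz is not to be determined. CL/F appears only in a list of λz-dependent parameters, which suggests the single-dose form Dose/AUC0-inf.

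That form is wrong for a drug at steady state, because AUC0-inf after a steady-state dose also contains what is left from earlier doses. Clearance would then be understated. Protocol Table 1 seems to show this happening elsewhere: at 200 mg once daily, Dose/AUC0-24 is well above the reported CL/F. LOXO-305 parameters sit in the primary endpoint list, so a missing or biased value would appear in the report under that label.

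**Working it through.** **Inputs.** LOXO-305 is given at 200 mg once daily on Days 6 to 19, with the cocktail on Day 15 (protocol 3.1), so the dosing interval is 24 h. The patient values are from protocol Table 1 (section 1.4.2): at 200 mg, AUC0-24 is 91,000 ng·h/mL (N=99), half-life 19.9 h (N=64) and CL/F 1.14 L/h (N=64). Neither document gives a planned CL/F value or formula for this trial, so there is no planned figure to reproduce.

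**Is Day 15 at steady state?** Nine doses precede it. With linear kinetics, the fraction of steady state reached is 1 − 2^(−9×24/t½). This is 99.9% at 19.9 h and 99.3% at 30.1 h, the longest half-life in Table 1.

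**CL/F from retained quantities.** Dose/AUC0-24 = 200 mg ÷ 91,000 ng·h/mL = 2.20 L/h. This uses neither λz nor AUC0-inf.

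**CL/F if AUC0-inf were used on the same profile.** For one compartment, AUC0-inf/AUC0-24 = 1/(1 − exp(−ln2 × 24/t½)).

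- At 19.9 h the ratio is 1.77, so CL/F would be 2.20/1.77 = 1.24 L/h.
- With first-order absorption (assumed rate constant 0.8 to 2 per h) the ratio is 1.78 to 1.80.
- Over the Table 1 half-lives (17.4 to 30.1 h) it is 1.62 to 2.36, or up to 2.40 with absorption.
- The extrapolated share at 19.9 h is 1 − 1/1.77, about 43%.

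**Does Table 1 show that form?**

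| Dose (mg) | Dose/AUC0-24 (L/h) | Reported CL/F (L/h) | Observed ratio | Ratio expected if AUC0-inf was used |
|---|---|---|---|---|
| 25 | 2.55 | 1.55 | 1.65 | 1.67 |
| 50 | 2.49 | 2.62 | 0.95 | 1.64 |
| 100 | 1.91 | 0.968 | 1.97 | 1.90 |
| 150 | 2.33 | 1.36 | 1.71 | 1.66 |
| 200 | 2.20 | 1.14 | 1.93 | 1.77 |
| 250 | 2.25 | 1.26 | 1.79 | 1.62 |
| 300 | 1.90 | 1.63 | 1.16 | 2.36 |

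Five rows agree to within about 10%; the 50 mg and 300 mg rows do not. The table comes from another study, in patients. Its 24-hour value was imputed from the predose sample, because sampling stopped at 8 h, and CL/F rests on fewer subjects than AUC0-24. It suggests how that study may have computed CL/F and says nothing about this SAP.

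**Reading the SAP table as a whole.** LOXO-305 loses λz, AUC0-inf, its extrapolation percentage and Vz/F, and keeps AUC0-24, Cmax and CL/F. That is the pattern of a steady-state analyte with CL/F = Dose/AUC0-24. To obtain the 1.8-fold error, an analyst would have to compute an AUC that the table excludes. That AUC would, at about 43% extrapolation, also exceed the 30% limit above which SAP 8.5.1.2 removes AUC0-inf values from descriptive statistics.

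**What uses these parameters?** The mixed model in SAP 8.5.3 compares AUC0-t, AUC0-inf, Cmax and the paraxanthine ratio for the probe drugs only. Protocol 1.4.2 relates exposure in healthy volunteers to the recommended Phase 2 dose through steady-state Cmax and AUC0-24. Neither depends on LOXO-305 half-life or CL/F.

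**The case for a change.** The strongest case for acting is that the only sentence in the SAP governing CL/F puts it behind the λz fit, with no exception, and the steady-state formula is written nowhere. Two programmers could follow the text and reach different results. Table 1 makes the wrong route plausible in this programme, and the remedy would be two lines with no new data. The SAP also shows single-dose habits elsewhere: 8.5.1.4 treats any measurable predose value as anomalous, although 8.5.1.3 expects a real LOXO-305 predose value on Day 15.

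The textual inconsistency stands, and half-life is its least settled part. The SAP does not say whether λz may be fitted for LOXO-305 without being reported. The rest is weaker. The list in 8.5.1.1 gives examples for five analytes and is not a formula for this one. SAP 8.5.1.3 refers to predose and 24-hour LOXO-305 samples on Day 15, so AUC0-24 is available. Whether any LOXO-305 profile is long enough for a sound λz cannot be judged, because its sampling times are redacted. A figure such as 1.1 half-lives for a 2 to 24 h fit, (24 − 2)/19.9, assumes a window the reader cannot see. SAP 8.5.1.1 already has the report discuss half-life robustness when the fitted span is below two half-lives.

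**Conclusion.** No change follows. SAP 8.5.1 and 8.5.1.1 do not fit together for LOXO-305 half-life and CL/F, but analysts would fill this gap sensibly. Dose/AUC0-24 is the standard steady-state clearance, needs nothing the table removes, and matches the pattern of exclusions. Half-life is either reported from an unlisted λz or left out, and the qualifiers on the parameter list allow both.

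The 1.8-fold understatement (1.6 to 2.4 over the Table 1 half-lives) is correct arithmetic for a calculation that neither document prescribes. It assumes linear one-compartment kinetics, steady state on Day 15 and half-lives like those in patients. Even if it occurred, it would affect one descriptive LOXO-305 parameter. The change in every probe geometric mean ratio and its 90% interval would be zero, as would the change in the Cmax and AUC0-24 exposure comparison.

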8.5.1.1. Criteria for the Calculation of Apparent Terminal Elimination Rate Constant and Half-life

The start of the terminal elimination phase for each subject will be defined by visual inspection and generally will be the first point at which there is no systematic deviation from the log-linear decline in concentrations.

The apparent terminal elimination rate constant (λ_z) will only be calculated when a reliable estimate can be obtained using at least 3 data points, preferably not including C_{max}, and the adjusted coefficient for determination of exponential fit (R²-adj) of the regression line is ≥ 0.7 . Parameters requiring λ_z for their calculation (eg, AUC_{0-inf}, t_{1/2}, CL/F, V_z/F, and MRT_{inf}) will only be calculated if the R²-adj value of the regression line is ≥ 0.7 .

The following regression-related diagnostic PK parameters will be determined, when possible:

Parameter	Units	Definition
λ_z Upper	h	end of exponential fit
λ_z Lower	h	start of exponential fit
λ_z N	NA	number of data points included in the log-linear regression
λ_z Span Ratio	NA	time period over which λ_z was determined as a ratio of $t_{1/2}$
R ² -adj	NA	adjusted coefficient for determination of exponential fit

Where possible, the span of time used in the determination of λ_z (ie, the difference between λ_z Upper and λ_z Lower) should be ≥ 2 half-lives. If the λ_z Span Ratio is < 2 , the robustness of the $t_{1/2}$ values will be discussed in the CSR.

8.5.1.2. Criteria for Calculation and Reporting of Area Under the Concentration-time Curve

The minimum requirement for the calculation of AUC will be the inclusion of at least 3 consecutive concentrations above the lower limit of quantification. If there are only 3 consecutive concentrations, at least 1 should follow C_{max} .

AUC_{0-inf} values where the percentage extrapolation is less than 30% will be reported. AUC_{0-inf} values where the percentage extrapolation is greater than 30% will be listed but excluded from descriptive statistics.

If AUC_{0-inf} cannot be determined reliably for all subjects, an alternative AUC measure, such as AUC to a fixed time point or AUC_{0-t} , may be used in the statistical analysis.

8.5.1.3. Criteria for Handling Below the Limit of Quantification or Missing Concentrations for Pharmacokinetic Analysis

Plasma concentrations below the limit of quantification (BLQ) will be assigned a value of 0 before the first measurable concentration and thereafter BLQs will be treated as missing. The following rules apply with special situations defined below:

- If an entire concentration-time profile is BLQ, it will be excluded from PK analysis.
- Where 2 or more consecutive concentrations are BLQ at the end of a profile, the profile will be deemed to have terminated and any further quantifiable concentrations will be set to missing for the calculation of the PK parameters, unless they are considered to be a true characteristic of the profile of the drug.
- If a predose plasma concentration is missing, it may be set to 0 by default, with the exception of LOXO-305 on Day 15. If the Day 15 predose plasma concentration of LOXO-305 is missing, the Day 15 24-hour concentration may be used as the predose concentration.

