4. STUDY DESIGN

This is a Phase 1, open-label, 2-period, fixed-sequence drug-drug interaction study to investigate the effect of multiple oral doses of LOXO-305 on the PK of single oral doses of caffeine (CYP1A2 substrate) and its metabolite paraxanthine, S-warfarin (CYP2C9 substrate), and omeprazole (CYP2C19 substrate) in healthy subjects.

In Period 1, Day 1, 200 mg caffeine (tablet), 40 mg omeprazole (capsule), and 10 mg warfarin (tablet) administered as a single dose of probe drug cocktail, along with 10 mg vitamin K (tablets), will be administered in the morning following a fast of at least 10 hours predose and 2 hours postdose. Blood samples for concentrations of the substrates (caffeine/paraxanthine, omeprazole, and S-warfarin) in plasma will be collected predose through 120 hours postdose on Day 1. Of these samples, samples will be analyzed for concentrations of caffeine/paraxanthine from predose through 24 hours postdose, for concentrations of omeprazole [REDACTED], and for concentrations of [REDACTED].

There will be a washout period of 5 days between administration of the probe drug cocktail on Day 1 and the first dose of LOXO-305 on Day 6.

[figure not shown]
In Period 2, on Days 6 through 19, oral doses of 200 mg LOXO-305 will be administered once daily (QD) for 14 consecutive days in the morning at the actual time of the Day 1 probe drug cocktail dosing (\pm 1 hour). On Day 15, LOXO-305 will be coadministered with 200 mg caffeine (tablet), 40 mg omeprazole (capsule), and 10 mg warfarin (tablet) administered as a single dose of probe drug cocktail, along with 10 mg of vitamin K (tablets) at the actual time of the Day 1 probe drug cocktail dosing (\pm 1 hour) following a fast of at least 10 hours predose and 2 hours postdose. On Days 7 through 11, and Days 13, 14, 16, 18, and 19, subjects will fast for at least 2 hours predose and 1-hour postdose. On Days 6, 12, and 17 where clinical laboratory evaluations are performed, subjects will fast for at least 8 hours predose and 1 hour postdose. Blood samples for concentrations of LOXO-305 in plasma will

CCI

CCI. Samples collected CCI. CCI LOXO-305 dosing CCI. Blood samples for concentrations of the substrates (caffeine/paraxanthine, omeprazole, and S-warfarin) in plasma will be CCI; of these samples, samples will be analyzed for concentrations of caffeine/paraxanthine from CCI, for concentrations of omeprazole CCI, and for concentrations of CCI.

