7.3. Pharmacokinetic Population

The PK population will consist of all subjects who have received a dose of LOXO-305 or the probe cocktail drugs, have at least 1 quantifiable plasma concentration, and for whom at least 1 PK parameter can be computed. A subject may be excluded from the PK summary statistics and statistical analysis if the subject has an AE of vomiting that occurs at or before 2 times the median t_{max} . The impact of protocol deviations on the PK population will be evaluated on a case-by-case basis.

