8.5.3. Pharmacokinetic Statistical Methodology

All PK concentrations and parameters will be listed.

Summary tables, mean (+ standard deviation [SD]) figures, overlaying individual figures, and individual figures by analyte and time postdose will be provided for plasma PK concentrations. All PK concentration figures will be produced on both linear and semi-logarithmic scales, with the exception of figures across all days, which will be produced on the linear scale only. The +SD bars will only be displayed on the linear scale.

Summary tables by treatment will be provided for all PK parameters, with the exception of diagnostic regression-related PK parameters. Summary statistics (n, Mean, SD, CV, minimum, median, maximum, geometric mean [Geom Mean] and geometric CV [Geom CV]) will be calculated for plasma LOXO-305, caffeine, paraxanthine, omeprazole and S-warfarin

PK parameters. Excluded subjects will be listed in the PK parameter tables, but will be excluded from the statistical analysis and summary statistics and noted as such in the tables.

A statistical analysis will be conducted to investigate the drug-drug interaction on the PK of the following comparisons:

- LOXO-305 plus caffeine (test) versus caffeine alone (reference) To test the drug-drug interaction on the PK of caffeine and paraxanthine
- LOXO-305 plus omeprazole (test) versus omeprazole alone (reference)
- LOXO-305 plus warfarin (test) versus warfarin alone (reference)

The natural log-transformed³ PK parameters (AUC_{0-t} , $\text{AUC}_{0-\text{inf}}$, C_{\max} , and MRAUC for paraxanthine only) will be analyzed using a mixed model.⁴ The model will include actual treatment as a fixed effect, and subject as a random effect.

For each PK parameter separately, the least squares mean (LSM) for each treatment, difference in LSMs between the test and reference treatments, and corresponding 90% confidence interval (CI) will be calculated; these values will then be exponentiated to give the geometric least squares mean, geometric mean ratios, and corresponding 90% CI.

Additionally, the pooled estimate (across all treatments) of the within-subject CV will be calculated, and residual plots will be produced to assess the adequacy of the model(s) fitted.

Examples of the SAS code that will be used are as follows:

Mixed Model Analysis

```
proc mixed data = <data in>;
  by parcatln parcat1 paramn param;
  class trtan usubjid;
  model lpk = trtan / cl residual ddfm = kr2;

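### Should the SAP's 30% extrapolation rule for AUC0-inf also cover the mixed model and CL/F, with the fallback AUC fixed in advance?

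*SAP*

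**What the plan says.** SAP 8.5.1.2 reports AUC0-inf when less than 30% is extrapolated. Above that, AUC0-inf "values where the percentage extrapolation is greater than 30% will be listed but excluded from descriptive statistics". The same section adds that if AUC0-inf "cannot be determined reliably for all subjects, an alternative AUC measure, such as AUC to a fixed time point" or AUC0-t, may go into the statistical analysis.

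SAP 8.5.1.1 makes AUC0-inf, half-life, CL/F, Vz/F and MRTinf depend on a reliable terminal slope from at least three points; they "will only be calculated if the R²-adj value of the regression line is" 0.7 or more. It also asks for a fitting span of at least 2 half-lives where possible, and for the study report to discuss half-life robustness when the span is shorter.

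SAP 8.5.3 states: "Summary tables by treatment will be provided for all PK parameters, with the exception of diagnostic regression-related PK parameters". It fits the log of AUC0-t, AUC0-inf and Cmax, plus the metabolite ratio for paraxanthine, without an extrapolation condition: "The model will include actual treatment as a fixed effect, and subject as a random effect". The result is a geometric mean ratio with a 90% confidence interval.

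For caffeine and paraxanthine on Day 1, SAP Section 4 says "samples will be analyzed for concentrations of caffeine/paraxanthine from predose through 24 hours postdose". SAP 8.5.1 nevertheless plans a paraxanthine-to-caffeine ratio on AUC0-48 where possible.

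**The concern.** The filter names one output only. When the SAP means both, it says so, as in Section 7.3: "A subject may be excluded from the PK summary statistics and statistical analysis if the subject has an AE of vomiting". A literal reader concludes that AUC0-inf values above 30% leave the table but stay in the model, and that CL/F, Vz/F and MRTinf from those profiles stay in the table.

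High extrapolation goes with slow elimination. If LOXO-305 slows a probe, the filter removes more co-administration values than probe-alone values. The table means would then suggest a smaller effect than the model and would not agree with the CL/F row beside them. An open fallback could also let the AUC be chosen after results are seen. At stake would be the credibility of a parameter in the primary analysis (protocol 8.3.2).

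**Working it through.** The plan has no figure to reproduce here: the sample size was set without statistical considerations (protocol 8.1), and probe half-lives are not given. Half-lives and variability below are assumptions.

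**1. When a profile is flagged.** For mono-exponential decline sampled to time T, the extrapolated fraction is f = 2^(−T/t½). Setting f = 0.30 gives T/t½ = log2(1/0.3) = 1.74. The threshold half-life is 24/1.737 = 13.8 h for a 24 h profile, 48/1.737 = 27.6 h for 48 h and 120/1.737 = 69.1 h for 120 h (the Day 1 collection window in SAP Section 4; the S-warfarin analysis window is redacted).

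**2. Share flagged and its effect, caffeine, 24 h, true ratio 1.25.** Assume between-subject CV 30% and within-subject CV 15%. The SD of log half-life is √(ln 1.09 + ln 1.0225) = 0.329. Take a median of 8 h alone, so 10 h with LOXO-305.

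- Co-administration: z = ln(13.82/10)/0.329 = 0.98, so 16% are flagged. Dropping them shifts the log mean by −0.329·φ(z)/Φ(z) = −0.097.
- Alone: z = ln(13.82/8)/0.329 = 1.66, so 5% are flagged; shift −0.035.
- Ratio implied by the table: 1.25 × exp(−0.097 + 0.035) = 1.17.
- Unfiltered CL/F × filtered AUC0-inf ÷ dose, co-administration: exp(−0.097) = 0.91.

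**3. Simulation.** This used 1,500 trials of 16 subjects, a one-compartment oral model, assay CV 10% and 13 assumed sampling times to 24 h. The model kept every value with adjusted R² of 0.7 or more.

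| True ratio | Half-life alone (h) | Model | Ratio implied by table |
|---|---|---|---|
| 1.25 | 4 / 6 / 8 | 1.25 / 1.25 / 1.25 | 1.25 / 1.22 / 1.17 |
| 2.0 | 4 / 6 / 8 | 1.99 / 2.00 / 1.98 | 1.91 / 1.67 / 1.47 |
| 1.0 | 4 / 6 / 8 | 1.00 | 1.00 |
| 0.5 | 4 / 6 / 8 | 0.50 | 0.50 / 0.50 / 0.52 |

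At 1.25 the flagged co-administration values were 0%, 4% and 19%, close to step 2. Over 120 h with assumed half-lives of 25, 35 and 45 h, a true 1.25 gave 1.25 in the model and 1.24, 1.20 and 1.15 in the tables.

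**4. Window.** A 400-trial rerun with caffeine sampled to 48 h, true ratio 1.25, gave 1.25, 1.26 and 1.25 in both model and tables, with 0%, 0% and 0.2% of co-administration values flagged. The Day 15 window is redacted.

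**5. What the plan already shows.** The table ratio and the CL/F product are not planned outputs; SAP 8.5.3 takes ratios only from the model. Its summaries include n, and the percentage extrapolated is a parameter in SAP 8.5.1, so it is listed and summarised. By step 1, a mono-exponential parent profile above 30% spans less than 1.74 half-lives. It therefore falls below the span of 2 at which SAP 8.5.1.1 requires discussion.

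**6. Fallback.** At a true 1.25 over 24 h, if the condition means every subject at or below 30%, it is met in 4%, 57% and 98% of trials. If it means only that a terminal slope can be fitted, the figures are 0%, 1% and 4%. The trigger is therefore loose. AUC0-t is modelled regardless; in its place AUC0-inf's 1.25 would read 1.22, 1.18 and 1.15.

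**The case for a change.** The strongest case for a change is that silence about a primary-analysis parameter invites an after-the-fact decision. An analyst who sees the table and model disagree might extend the filter to the model, which would pull an inhibition effect toward 1. Two or three sentences would prevent this at almost no cost. Paraxanthine is the hardest case: with a half-life assumed equal to caffeine's and no interaction, 10%, 62% and 93% of its 24 h AUC0-inf values would be flagged or not calculable. The span check in step 5 does not protect it, because a metabolite with its parent's rate constant reaches 30% at a half-life of only 6.8 h, from (1 + x)e^(−x) = 0.3, x = 2.44.

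The textual reading stands, and so does the loose trigger. The need for a change does not. The literal reading is also the sensible one, and substantial deviations from the SAP must be identified in the study report (SAP Section 1). Extending the filter to CL/F would spread the selective loss of slow profiles to rows that now escape it. For paraxanthine, a fixed choice between the two modelled measures gives no clean answer. With caffeine clearance halved and a true paraxanthine ratio of 1.00, AUC0-inf with all values gives 1.04, 1.10 and 1.17, while AUC0-t gives 0.82, 0.73 and 0.68. Both will be reported. Paraxanthine is also not among the three substrates named in the primary objective.

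**Conclusion.** No change to the plan is needed. The SAP leaves a detail unstated, and analysts following it as written fill it in the better way: evaluable AUC0-inf values stay in the model, and the interaction ratio for the parent probes is then close to unbiased (1.25 for a true 1.25; 1.98 to 2.00 for a true 2.0 over 24 h). The discrepancy is confined to descriptive rows. At a true 1.25 over 24 h it is between nothing and 0.08 on the ratio scale (1.25 against 1.17), and sampling to 48 h removes it. Larger gaps need a doubling of exposure, whereas protocol 1.3 and 1.5 report at most weak in vitro inhibition of the three enzymes studied. No no-effect margin is tested, and SAP 8.1 already urges caution because the study is not powered.

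These sizes rest on assumed half-lives, variability and sampling times, a one-compartment model and partly redacted windows. A footnote that CL/F, Vz/F and MRTinf are unfiltered could sit in the table shells, which are a separate document not available here. The fallback wording is loose, most visibly for paraxanthine, but tightening it would not alter the planned estimate for caffeine, omeprazole or S-warfarin.
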